**Study Plan/SAP**

1. Title, academic degree, name and surname, and place of employment of the applicant:

*Dr hab. n. med. [name]  
Uniwersyteckie Centrum Rehabilitacji (UCR)  
[name]*

2. [contact]**

3. Name of the organizational unit of the Wroclaw Medical University implementing the project:

*Uniwersyteckie Centrum Rehabilitacji – place of data collection and analysis  
USK - Szpital Tymczasowy na [name] - place of surveys; possibly additional centers after their authorities' decision that will not impact study design (only for Team members).*

4. Project title: **Physical Activity and the Course of COVID-19.**

*- in hospitalized patients*

5. Registration number of the Center for the Support of Science of the Wroclaw Medical University - **none**

6. Detailed description of the project together with justification of its purposefulness and feasibility assessment:

*Physical activity is one of the factors modulating human immunity and affecting general efficiency, including respiratory one. For this reason, its level may be associated with the severity of the course of COVID-19.*

*The study aims to assess the relationship between physical activity levels before the onset of COVID-19 and the course of the disease. The course of the disease is often surprising and independent of selected poor prognostic factors; therefore, it is advisable to look for relationships between those variables that have not yet been analyzed.*

**Methodology:**

*The study consists of a survey on physical activity prior to contracting COVID-19 among patients hospitalized due to this disease at the USK (Temporary Hospital for COVID patients).*

*Time Frame: 01 Nov 2021- throughout the entire period of hospital activity*

**Inclusion criteria:**

- *adult*
- *sex – any*
- *race – any*
- *confirmed COVID-19 infection and hospitalization in the COVID-19 treatment unit*

**Exclusion criteria:**

- pregnancy;*
- inability to complete the questionnaire during hospitalization or up to a week after discharge;*
- history of a significant cardiovascular event in the last 6 months (acute coronary syndrome, stroke, amputation, revascularization of peripheral vessels, pulmonary or peripheral embolism of any etiology) if the patient did not complete the rehabilitation process;*
- symptomatic chronic respiratory disease not responding to therapy before hospitalization for COVID-19 (or no therapy);*
- any dyspnea at rest in the last month before COVID-19;*
- injury to the locomotor system in the last month before contracting COVID-19;*
- hospitalization in the last month before contracting COVID-19.*

*In order to describe the group and analyze the survey results, information from the patient's interview, physical examination, and the results of basic and additional tests contained in the patient's hospital documentation during the stay due to COVID-19 will be used.*

*The International Physical Activity Questionnaire (IPAQ) short form will be used to determine the level of physical activity.*

*After consenting to participate in the study, the patient will be asked to answer 7 survey questions. If the patient's condition prevents participation in the survey, the patient will be allowed to participate on a different day, including within 7 days from discharge, or indicate a relative who can fill out the survey for the patient.*

*Each patient will be given an identification number, and the list of participants will be prepared.*

*Data from medical records will be prospectively collected for Primary Outcome Measures: death due to COVID-19, recovery – patients discharged home, transfer to intensive care unit (ICU), and Secondary Outcome Measures: hospitalization length before transfer to intensive care unit, laboratory tests. Additional data – lab results, comorbidities, pharmacotherapy history, and complications related to hospitalization – will be collected if available.*

*Then, they will be combined with the IPAQ results (the surveys will be analyzed anonymously, and paper version of IPAQs will be archived in Uniwersyteckie Centrum Rehabilitacji, [name]) in one document (Excel, based on the patient number).*

*Data ready for statistical analysis will be sent to a statistician and analyzed according to the Statistical Analysis Plan (SAP).*

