*There is no information in the literature on the impact of daily physical activity (obtained directly from patient questionnaires) on the course of COVID-19. Learning what relationships (if any) exist between them can help plan the prevention of this infectious disease and assess the strength of behavioral actions with their impact on the prognosis.*

Additional documents (underline as appropriate)

- a copy of the Rector's decision to grant funding as part of the statutory activities of the University
- information for persons participating in a medical experiment containing detailed data on the purposes and principles of conducting the research, expected therapeutic and other benefits for these persons, and the risk associated with participation;
- a written commitment signed by the researcher to obtain informed consent from all test subjects or their legal representatives;
- a template of the patient's or their legal representative's consent form, which contains statements regarding:
  - voluntary consent to participate in the medical experiment after reading the information,
  - confirmation of the right to ask the researcher questions and receive answers to these questions,
  - information about the possibility of withdrawing from participation in the study at any stage;
- information on the method of collecting and processing personal data for the person participating in a medical experiment;
- research insurance information;
- consent of the person participating in a medical experiment or their legal representative to the processing of data relevant to participation.
- consent of the Head of the USK Temporary COVID Hospital/s (available at the Bioethics Committee office)
- IPAQ – polish version-  
[https://www.academia.edu/19229070/Mi%C4%99dzynarodowy\\_Kwestionariusz\\_Aktywno%C5%9Bci\\_Fizycznej\\_IPAQ\\_wersja\\_polska](https://www.academia.edu/19229070/Mi%C4%99dzynarodowy_Kwestionariusz_Aktywno%C5%9Bci_Fizycznej_IPAQ_wersja_polska)

Head  
of the organizational unit  
implementing the project

.....  
Signature, stamp

Applicant

.....  
Signature, stamp

Wrocław, .....

---

References:

Brodin P. Immune determinants of COVID-19 disease presentation and severity. *Nat Med.* 2021 Jan;27(1):28-33. doi: 10.1038/s41591-020-01202-8. Epub 2021 Jan 13. PubMed ID: 33442016

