## Statistical Analysis Plan

Sample size calculation for confidence interval: 95%; fraction size: 0.5; max error: 5%: 384 participants.

The variables subjected to statistical analysis will be on nominal scales – including dichotomous ones – and ratio scales:

- variables expected in the ratio scales: raw MET, hospitalization length, age, BMI, and concentration levels of all biochemical factors studied;

- variables expected in dichotomous scales: sex, oxygen therapy need (Yes/No), information about patient death or transfer, information about complications, variables describing the study group in terms of history and comorbidities, and medication groups.

The variables in the interval scales are nicotine addiction and IPAQ level (the latter will be treated as a directional, three-item interval variable).

Statistical analysis will begin by verifying the accuracy of the data contained in the compiled database. For this purpose, descriptive statistics with histograms will be determined for ratio variables and tables of sample sizes for nominal variables. Then all extreme outliers and dubious results will be verified again with the source materials. Gaps found in the database will not be replaced with any other values.

In the case of variables on ratio scales, their normality of distribution will be assessed. The Shapiro-Wilk W test will determine the normality of distribution. Characterization of this group of variables will be based on the statistical significance of the W-test. The following descriptive statistics will be defined for variables with a normal distribution: size, mean value, standard deviation, and 95% confidence interval for the mean value. While size, median, and range will be determined for variables that are not normally distributed.

The Shapiro-Wilk W test with a significance level of  $\alpha=0.05$  will be used to evaluate the normality of distributions.

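### Patients with long-standing immobility stay eligible, would count as low activity and are not identified, so an activity–outcome association could partly reflect inability to be active

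*Combined protocol and SAP*

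**What the plan says.** The Inclusion criteria admit any adult with confirmed COVID-19 hospitalized in the treatment unit. The Exclusion criteria then remove several groups whose activity is likely to have been limited by illness:

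- "injury to the locomotor system in the last month before contracting COVID-19";
- "hospitalization in the last month before contracting COVID-19";
- "any dyspnea at rest in the last month before COVID-19";
- "history of a significant cardiovascular event in the last 6 months" (stroke and amputation are among the events listed), but only "if the patient did not complete the rehabilitation process";
- "symptomatic chronic respiratory disease not responding to therapy before hospitalization for COVID-19 (or no therapy"), which carries no 1- or 6-month window.

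Activity is measured with the IPAQ short form, and the SAP treats the IPAQ level as three ordered levels. The protocol will use interview, physical examination and test results from the hospital record, and will collect comorbidities if they are available. The SAP lists "variables describing the study group in terms of history and comorbidities, and medication groups" among its yes/no variables. Neither the protocol nor the SAP names an item on walking ability, disability or frailty before COVID-19.

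For outcomes, the SAP plans principal component analysis, correlations, chi-squared tests with odds ratios for 2x2 tables, group comparisons and a Cox model for the IPAQ value. It names no covariates, restriction or sensitivity analysis for the IPAQ comparisons. The paragraph on the expected use of the results says they can help plan prevention and "assess the strength of behavioral actions with their impact on the prognosis".

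**The concern.** The exclusions show that the investigators saw forced inactivity as a problem for the exposure. They deal with it mainly where the cause is recent. A patient who has been bed-bound or wheelchair-dependent for years meets none of the listed exclusions on that ground and would report little or no activity.

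The lowest IPAQ level would then mix people who could not be active with people who could have been but were not. If immobile patients have a worse prognosis for reasons unrelated to behaviour, low activity will be associated with death or ICU transfer even when activity has no effect. As an association, that result is accurate. Read as the strength of a behavioural action, it is partly wrong. With no mobility item recorded, a reader could not tell how much of the association comes from this source.

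**Working it through.** **1. Reach of each exclusion.**

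| Criterion | Window | Long-standing immobility covered? |
|---|---|---|
| Locomotor injury | 1 month | No |
| Hospitalization | 1 month | Only if also admitted in that month |
| Dyspnea at rest | 1 month | Some chronic cardiopulmonary patients; not neurological or orthopaedic causes |
| Cardiovascular event, including stroke and amputation | 6 months, rehabilitation not completed | No: older events, and recent ones with rehabilitation completed, stay eligible |
| Uncontrolled or untreated symptomatic chronic respiratory disease | No 1- or 6-month limit | Yes, respiratory causes only |

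Immobility from an old stroke, an old amputation, joint disease or frailty is therefore not excluded as such.

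**2. The plan's own figure.** The SAP's sample size is a precision calculation for one proportion: n = 1.96² × 0.5 × 0.5 / 0.05² = 384.1, which reproduces the stated 384. It does not depend on this point and gives no protection against it, because bias does not shrink with n.

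**3. Illustration of size.** Every rate here is an assumption, since the documents give none:

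- activity has no true effect;
- mortality is 10% in mobile patients at every activity level;
- 40% of mobile patients are low-activity;
- all immobile patients are low-activity (the documents do not reproduce the IPAQ scoring rule);
- p is the immobile share of the cohort and m is mortality in immobile patients.

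IPAQ is collapsed to low versus other, so that a 2x2 table and a crude odds ratio (OR) can be formed.

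Risk in the low group = [p·m + (1−p)·0.40·0.10] / [p + (1−p)·0.40]; risk in the rest = 0.10.

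Example, p = 0.05 and m = 0.25: (0.0125 + 0.0380) / (0.05 + 0.38) = 0.0505 / 0.43 = 0.1174. OR = (0.1174/0.8826) / (0.10/0.90) = 1.20.

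| Immobile share p | Mortality m | Crude OR | Chi-squared rejections, n = 384 |
|---|---|---|---|
| 1–3% | 15–20% | 1.01–1.08 | about 5–6% |
| 5% | 20% | 1.13 | about 7% |
| 5% | 25–35% | 1.20–1.33 | about 9–15% |
| 10% | 25–35% | 1.38–1.64 | about 17–36% |
| 15% | 25–35% | 1.54–1.93 | about 28–59% |

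Rejection rates are simulated with the uncorrected Pearson chi-squared test at the two-sided 5% level; the nominal rate is 5%. At p = 15%, immobile patients make up 0.15 / (0.15 + 0.85 × 0.40) = 0.15 / 0.49 = 31% of the low-activity group.

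**4. Whether the planned analyses separate these patients.** They do not. The chi-squared tests, group comparisons and Cox model use the IPAQ level or value with no named restriction or covariate. Principal component analysis describes joint variation among recorded variables; it does not remove confounding by a variable that was not recorded.

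**The case against.** **The bias may be negligible.** With 1–3% immobile and modest excess mortality, the OR is at most 1.08 and the error rate close to nominal. The top of the range needs nearly a third of the low-activity group to be immobile with 3.5 times the baseline mortality, and nothing in the documents suggests that. This stands: the upper figures show what is possible, not what is expected.

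**The exclusions are not purely recent.** This also stands. Chronic respiratory disease is excluded without a time window if uncontrolled or untreated, and the rest-dyspnea criterion removes some other chronic patients. The gap concerns the remaining causes.

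**The stated aim is a relationship, not a causal effect.** An immobile patient's low IPAQ score is correctly classified, and the behavioural wording describes possible usefulness. That is fair, and it confines the problem to interpretation. But the behavioural reading is one the protocol itself offers.

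**Other data may help.** Age, BMI, history, comorbidities and physical examination are available or may be. A reader might infer that adjustment for age and yes/no comorbidities could not remove the bias. The documents do not support that, and the illustration compares crude risks only, so it does not test it. Adjustment might remove part. It may also leave residual bias, since one diagnosis can cover both mobile and immobile patients. The SAP specifies no such adjustment for the IPAQ analyses. Examination findings may show paralysis or amputation, but that is not a systematic record of walking ability before COVID-19.

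**One walking item does not separate inability from choice.** Correct. Patients limited by heart failure, arthritis or frailty who still walk unaided would remain in the restricted set.

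**Conclusion.** The gap is clear from the text: apart from uncontrolled or untreated chronic respiratory disease, the exclusions for activity-limiting conditions reach back only 1 to 6 months, mobility before COVID-19 is not a named variable, and no planned analysis isolates immobile patients. An association between low activity and poor outcome could therefore partly reflect inability to be active.

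Its size cannot be derived from the documents. Under the stated assumptions the crude OR runs from about 1.01 to 1.93 with no true effect, depending mainly on how many immobile patients are enrolled and how much worse they do. A reader might infer that the study will report a false activity effect, or that any association found must come from immobile patients. Neither follows. The supportable conclusion is that the plan as written could not distinguish a negligible contribution from a material one, and that this matters for the behavioural interpretation.

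**What to change.** 1. Record one yes/no item with the IPAQ: whether the patient walked independently, without another person or a wheelchair, before COVID-19. The patient, a relative or the records can supply it; because it concerns status before COVID-19, it may also be recoverable for patients already surveyed.
2. Prespecify in the SAP a sensitivity analysis that repeats the IPAQ–outcome analyses in independently mobile patients, reported beside the full-cohort results.
3. State in the SAP that a behavioural interpretation requires the association to persist in that subset, and that the restriction reduces but does not eliminate confounding by functional limitation. Persistence is necessary for the behavioural reading, not sufficient.

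The cost is one extra question and a somewhat smaller restricted sample: with 384 enrolled, about 365 if 5% are immobile (384 × 0.95) and about 326 if 15% are (384 × 0.85). Eligibility and the full-cohort analyses do not change.

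### IPAQ answers given after discharge or by a relative are pooled with in-hospital self-reports without a flag or sensitivity analysis, so error in the exposure may depend on the outcome

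*Combined protocol and SAP*

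**What the plan says.** The survey procedure stands in the Study Plan, in the text after the exclusion criteria. The exposure has one source: "The International Physical Activity Questionnaire (IPAQ) short form will be used to determine the level of physical activity". Most patients would answer in hospital after consenting. For the others the plan provides: "If the patient's condition prevents participation in the survey, the patient will be allowed to participate on a different day". That day may fall after the stay, and someone else may answer in the patient's place; the wording is "including within 7 days from discharge, or indicate a relative who can fill out the survey for the patient". One exclusion criterion bears on the same situation: "inability to complete the questionnaire during hospitalization or up to a week after discharge". It does not say who has to complete the form.

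The same text names three primary outcomes: COVID-19 death, discharge home as recovery, and ICU transfer. The justification describes the exposure as "physical activity (obtained directly from patient questionnaires) on the course of COVID-19", which does not fit an answer given by a relative.

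The SAP gives its variables by scale. The first list reads "variables expected in the ratio scales: raw MET, hospitalization length, age, BMI, and concentration levels of all biochemical factors studied". The second list begins "variables expected in dichotomous scales: sex, oxygen therapy need (Yes/No), information about patient death or transfer, information about complications" and goes on to history, comorbidities and medication groups. Nicotine addiction and the three-level IPAQ category are named separately. None of these is the respondent, the completion date, or the order of survey and outcome. The methods that follow (correlations, chi-squared tests with odds ratios, a Cox model on the IPAQ value, and group comparisons) are not stratified or restricted by respondent or timing.

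**The concern.** The route by which the exposure is measured depends on how ill the patient is. A relative may judge the patient's earlier activity differently from the patient, and may know of an ICU transfer when answering. A patient who answers after going home already knows that the illness ended well. If either kind of answer carries a different error from in-hospital self-report, and the routes are used unequally across outcome groups, the misclassification is differential. It can produce an association between activity and disease course where none exists, or mask a real one.

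Adjusting for age, BMI or comorbidity would not remove this, because the fault lies in the recorded exposure. Analysing the surveys anonymously does not help either, because it is the respondent who knows the outcome. If respondent and date are not kept, the question cannot be examined afterwards.

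**Working it through.** **The plan's own figure.** The SAP gives 384 participants for 95% confidence, a proportion of 0.5 and a maximum error of 5%: n = 1.96² × 0.5 × 0.5 / 0.05² = 384.16. The 384 reproduces. It is used here only as the total.

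**Who uses which route.**
- *Another day, still in hospital:* may come before or after an ICU transfer.
- *Within 7 days after discharge:* open only to patients who left hospital alive, so mostly the discharge-home group, with that outcome known.
- *Relative:* triggered by the patient's condition, so plausibly concentrated in the sickest patients.

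**Illustration.** Apart from 384 and the three IPAQ levels, every input is an assumption:
- no true association (true odds ratio 1);
- 15% of 384 severe: 0.15 × 384 = 57.6, taken as 57, leaving 327;
- true low activity 50% in both groups;
- late or relative completion in 50% of severe patients;
- 20% of those answers understated by one IPAQ class.

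The share of severe patients affected is 0.5 × 0.2 = 0.10. The comparison is low against not low, by the two-sided two-proportion z-test at 0.05.

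*Upper case: everyone who is not low is moderate.* One class down always lands in low. Reported low activity in the severe is 0.5 + 0.5 × 0.10 = 0.55. Odds ratio = (0.55/0.45) / (0.50/0.50) = 1.22; type I error 11%.

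*Even split: 25% moderate, 25% high.* Only the moderate patients cross into low. Reported low activity is 0.5 + 0.25 × 0.10 = 0.525. Odds ratio = 0.525/0.475 = 1.11; type I error 6%.

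*Use of these routes by non-severe patients, upper case.*

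| Non-severe late or by relative | Reported low, non-severe | Odds ratio | Type I error |
|---|---|---|---|
| 0% | 0.50 | 1.22 | 11% |
| 20% | 0.5 + 0.5 × 0.2 × 0.2 = 0.52 | 1.13 | 7% |
| 30% | 0.5 + 0.5 × 0.3 × 0.2 = 0.53 | 1.08 | 6% |
| 50% (equal use) | 0.55 | 1.00 | 5% |

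*Opposite direction.* If the affected 10% of severe patients have activity overstated by one class, low becomes moderate: 0.5 − 0.5 × 0.10 = 0.45. Odds ratio = 0.45/0.55 = 0.82; type I error again 11%.

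*Range of assumptions, no use by non-severe patients.* With 30% to 70% late or by relative and 10% to 30% understated, the upper case runs from 0.5 + 0.5 × 0.03 = 0.515 (odds ratio 1.06, type I error 6%) to 0.5 + 0.5 × 0.21 = 0.605 (odds ratio 1.53, type I error 31%). With the even split, the top of that range falls to 0.5 + 0.25 × 0.21 = 0.5525: odds ratio 1.23, type I error 11%.

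**The case against.** Three stronger readings are tempting, and the documents support none of them.

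A reader might infer that late and relative-completed answers alike belong to patients who go to ICU or die. The post-discharge window cannot be used by someone who died in hospital, and discharge home is itself a primary outcome. Only the relative route plausibly concentrates in the worst cases. Even there, the patient consents and names the relative, which limits its use among the very sickest.

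A reader might infer that the error does depend on the outcome and exaggerates a link between low activity and a poor course. The documents show only that the route depends on the patient's condition. They do not show that these answers are wrong, or in which direction. The illustration goes to 1.00 with equal use and below 1 with overstatement.

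A reader might take the exclusion criterion and the relative provision as a contradiction. They share the one-week limit and read coherently together if a patient is excluded only when no permitted route yields a questionnaire. What remains is an ambiguity about whether a relative's completion counts.

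It is also fair to say that the data-collection form is not part of the documents. A date or respondent may be noted on the archived paper questionnaires, which are linked by patient number. That would make the fix easier. It would not supply the missing analysis, and the SAP's variable lists do not carry such a field forward.

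**Conclusion.** The point holds as a gap in design and analysis. Followed as written, the plan mixes three kinds of answer in its only exposure measure, lets the kind depend on illness and sometimes follow the outcome, and specifies nothing by which the effect could be seen. Exposure error may therefore depend on the outcome, in either direction.

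Its size is not known. The illustrative distortion is modest at the central assumptions and disappears when both groups use these routes equally. It rests on assumed severity, prevalence, route use and misreporting, and on reducing IPAQ to two classes; it does not model the planned Cox analysis. Confidence is medium: the omission is plain in the text, the bias is only plausible. The change should be made because it is cheap and because the information is hard to recover later.

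**What to change.** 1. Record for each questionnaire the completion date, the respondent (patient or relative), and the patient's status at completion: before or after ICU transfer, discharge or death. Add these to the SAP's variable lists.
2. Report IPAQ level by respondent and timing within outcome groups.
3. Pre-specify a sensitivity analysis restricted to self-reports completed before any outcome.
4. State in the exclusion criterion whether a relative's completion counts as completing the questionnaire, and bring the description of activity as reported directly by patients into line with that.

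No change to the recall period is asked for: the Methodology already sets it as before contracting COVID-19, and the questionnaire wording is not in the documents.

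The cost is three fields on the form, one table and one extra analysis. The restricted analysis is smaller and loses the sickest patients, so it should be read beside the full analysis and not replace it. The relative route can stay, since removing it would lose the same patients.

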Principal component analysis (PCA) will assess global relationships between the key variables, regardless of scale. PCA additionally allows the identification of non-obvious and difficult-to-predict correlations between analyzed variables on different measurement scales. The developed PCA model will be estimated using the NIPALS algorithm. The convergence criterion will be set at 0.00001, and the maximum number of iterations will be 100. The number of components will be determined by establishing the maximum predictive ability of  $Q^2$  using V-fold cross-validation, adopting  $V_{max}=7$ . The optimal PCA model will be reduced to principal components, and the results will be presented in a graph, including the contribution of each component to the overall percentage of explained variance and information on their statistical significance.

Pearson correlation coefficient matrices and Spearman's rank correlation coefficients will be calculated to determine correlations between variables of ratio scales.

Their statistical significance will be determined with a t-test adopting a significance level of  $\alpha=0.05$ .

The basis for assessing the correlation of nominal variables will be the significance of Pearson's chi-squared test. In the case of dichotomous variables, for which it will be possible to construct bivariate (2x2) tables, an additional odds ratio (OR) will be determined, along with a 95% confidence interval (OR $\pm$ 95%CI).

A nonparametric Cox proportional hazards model will be used to evaluate the effect of the IPAQ value on survival probability.

The data analysis will also involve testing the statistical significance of differences between mean values: the parametric Student's t-test for independent samples and parametric analysis

of variance (ANOVA) with the post-hoc least significant difference (LSD) test for variables that meet the normality of distribution and homogeneity of variance assumptions, or the nonparametric Mann-Whitney U-test and nonparametric Kruskal-Wallis ANOVA for variables not meeting these assumptions. In addition, Levene's test and the Brown-Forsythe test will assess the homogeneity of variance.

A significance level of  $\alpha=0.05$  will be assumed for all statistical analyses.

Statistical analysis will be performed using StatSoft's Statistica 13.3 PL.

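### The SAP's hospitalization length is undefined, does not match the protocol's stay-before-ICU outcome, and is tested as an ordinary number with no rule for stays ended by death or transfer

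*Combined protocol and SAP*

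**What the plan says.** In the study plan, the outcome measures follow the exclusion criteria. The primary outcomes are death from COVID-19, discharge home and ICU transfer. The secondary outcomes are laboratory tests and "hospitalization length before transfer to intensive care unit".

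The Statistical Analysis Plan does not repeat that definition. Its list of ratio variables begins "raw MET, hospitalization length, age, BMI". No start, end or population is given for the stay. Ratio variables go to two kinds of analysis:

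- Correlation: "Pearson correlation coefficient matrices and Spearman's rank correlation coefficients will be calculated to determine correlations between variables of ratio scales".
- Group comparison, described as "testing the statistical significance of differences between mean values": t-test or ANOVA, or Mann-Whitney or Kruskal-Wallis where the assumptions fail.

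The bad endings appear separately among the dichotomous variables, as "information about patient death or transfer", and are not linked to the stay. The only time-to-event method is a Cox model for survival by IPAQ value, with no censoring or competing-event rule. Missing values are not replaced.

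**The concern.** The protocol outcome and the SAP variable do not match, and neither available reading gives a usable comparison.

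**Days counted in all patients.** Discharge home is a good ending and death a bad one, yet both stop the count. If the clock also stops at ICU transfer, a second bad ending is mixed in. If less active patients die or are transferred more often and early, their stays look shorter and inactivity looks favourable. A genuinely faster recovery in active patients can be masked in the same way.

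**The protocol wording taken literally.** The value exists only for patients who reach the ICU. Because gaps are not filled, everyone else drops out, and the comparison is made within a group selected on a primary outcome. Copying the protocol phrase into the SAP would therefore not solve the problem.

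**Working it through.** **The plan's own figure.** The sample size is a single-proportion precision calculation: n = 1.96² × 0.5 × 0.5 / 0.05² = 384.16, so the stated 384 reproduces. It does not depend on length of stay.

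**Literal reading.** 384 × 0.05 = 19.2 and 384 × 0.15 = 57.6, so about 19 to 58 transferred patients at an assumed 5% to 15% transfer rate. Spread evenly over three IPAQ levels, that is about 6 to 19 per level.

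**All-patient reading, by arithmetic.** All inputs here are assumptions, because the documents give no rates or times. Let t be the day on which a bad exit ends the count, p the proportion with a bad exit, and 10 days the stay of those who go home, in both groups. Mean stay = p × t + (1 − p) × 10. With p = 30% (low activity) and 10% (high activity):

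| Bad exit on day | Low activity | High activity |
|---|---|---|
| 3 | 0.3×3 + 0.7×10 = 7.9 | 0.1×3 + 0.9×10 = 9.3 |
| 5 | 8.5 | 9.5 |
| 8 | 9.4 | 9.8 |
| 12 | 10.6 | 10.2 |

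Recovery is identical by construction, yet the group with more bad outcomes appears to stay less long until bad exits come later than discharge.

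**All-patient reading, by simulation of the Mann-Whitney test.** Stays are lognormal: median 10 days and log-SD 0.5 for discharge home, log-SD 0.6 for bad exits. The test is two-sided at 5%, with at least 1,000 replicates per scenario. Group sizes are 384/2 = 192, or 384/3 = 128 for three equal IPAQ levels. The table gives the share of trials in which the low-activity group is significantly shorter. By chance this would be about 2.5%.

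| Bad exits, low vs high | Per group | Day 3 | Day 5 | Day 8 | Day 12 |
|---|---|---|---|---|---|
| 30% vs 10% | 192 | 85% | 54% | 11% | under 1% |
| 30% vs 10% | 128 | 68% | 41% | 9% | under 1% |
| 22% vs 10% | 192 | 44% | 24% | 6% | 1% |
| 10% vs 5% | 192 | 11% | 8% | 4% | 2% |

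**Masking of a true benefit.** Suppose active patients really go home 10% sooner (9 versus 10 days), with 192 per group. With no bad exits, about 51% of trials are significant. With 22% versus 10% bad exits at day 3, about 5% are, and most of those point the wrong way. With bad exits at day 8, right-direction power is about 27%. At day 12 it is about 59%, above the starting value.

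**The case against.** A reader might infer that the SAP analyses total hospital stay. It does not say so. The label is short and could be shorthand for the protocol outcome. What the text supports is an undefined variable that is not aligned with the protocol.

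The distinction matters for the mechanism. If ICU days are counted, transfer does not shorten the stay and may lengthen it. The bad exits in the tables would then be deaths only. The argument from death stands on either reading.

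A reader might also infer that the result will reverse. The tables show that this needs bad exits that are both early and fairly frequent. With late exits the effect disappears, and power can even rise. Enrolment may also thin out the earliest events, since patients who cannot complete the questionnaire in hospital or within a week of discharge are excluded. A relative may answer instead, so this softens the point without removing it.

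The plan nowhere says that a shorter stay is better. For time to ICU, a shorter value would naturally be read as faster deterioration, so reversal is not the problem on that reading. Selection of transferred patients is. Finally, the SAP's tests are a general list, and the use of each one for length of stay is inferred from its classification as a ratio variable.

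These objections limit the size and certainty of the effect. They do not supply a definition or a rule for death and transfer.

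**Conclusion.** The point holds as a mismatch between protocol and SAP, combined with an unsuitable analysis. It is not evidence that the study's finding will be reversed. Without a rule for competing endings, a difference in hospitalization length between IPAQ levels cannot be interpreted, and its sign may depend on when deaths and transfers happen.

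The possible distortion runs from near chance to dominant across the assumed timings and rates, and nothing in the documents narrows that range. Confidence is high on the definition and the method, and moderate at most on the magnitude.

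This is a secondary outcome. Comparisons of death, discharge and ICU transfer as yes/no outcomes are not touched. The change should be made before analysis, but the study does not stand or fall by it.

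**What to change.** 1. Define the variable in the SAP: start (admission), end, population, and whether ICU days count.
2. Analyse time from admission to ICU transfer in all patients by IPAQ level, with ward death and discharge as competing events. Report cumulative incidence and a cause-specific Cox model.
3. If length of stay is kept, analyse time to discharge home alive, with patients who die counted as never discharged.
4. Report raw days only descriptively, separately by outcome, and remove them from the correlations and from the t-test/ANOVA and rank comparisons.

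The cost is SAP wording, modest extra analysis, and recording the dates of admission, transfer, death and discharge. The study plan already draws on hospital documentation but lists no date fields, so the data sheet should be checked for them. No change to sample size or recruitment follows.
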